8.4. Data Sources

The data source the medical record reviews will be patient records.

8.5. Study Size

Table 2. Sample Size for Medical Record Review

Country	Approximate Number of Physicians*	Number of Patient Records
Argentina (complete*)	41	469
Mexico (complete*)	15	99
Chile (complete*)	1	8
Costa Rica + Panama (complete*)	7	41
Peru (complete*)	5	30
Colombia	30-40	200
Total (approximate):	99-109	790-890

*Actual number of physicians/records where country complete

The objectives do not state any hypotheses and therefore, do not require any statistical testing. All the analyses will be descriptive and so sample size calculations are not required.

8.6. Data Management

Physician reported data from the eCRF will be transferred to a single electronic database. All data will be de-identified and anonymized. Incomplete data may be excluded from analysis following discussion with Pfizer.

De-identified raw data files will be transferred to Pfizer by a secure FTP site.

Analyses will be conducted in STATA statistical software version 14.1 (StataCorp, 2016. Stata statistical software: Release 14. College Station, TX, StataCorp LP).

8.7. Data Analysis

Detailed methodology for summary and statistical analyses of data collected in this study will be documented in a Statistical Analysis Plan (SAP), which will be dated, filed and maintained by the sponsor. The SAP may modify the plans outlined in the protocol; any major modifications of primary endpoint definitions or their analyses would be reflected in a protocol amendment.

All analyses are to be descriptive and so all methods to be used will reflect this descriptive nature. The specific method that will be used depends on type of variable being analyzed and those methods are:

- Categorical variables – will be described using:
 - Number of observations (n);
 - Number and percent (%) within each category;
 - Number of missing observations.
- Numeric variables – will be described using:
 - Number of observations (n);
 - Mean & Standard deviation;
 - Minimum, Maximum, Median and 1st & 3rd Quartiles;
 - Number of missing observations.
- Time to event – will be described using:
 - A Kaplan-Meier chart that will visually estimate the distribution of times to some events, eg, progression, and will take into account those patients for which the event has not as yet occurred;

- 1-yr and 2-yr rates, median or some more appropriate percentiles if the median time is not reached in the sample.

The analyses will be conducted (using the methods above) in a number of phases, as already detailed in the [Study Design](#) section.

Missing data will be excluded on a case by case basis and will not be imputed. This will mean that each table will not necessarily be based on the same number of patients.

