**TREATMENT PATTERNS AND CLINICAL OUTCOMES AMONG PATIENTS IN
LATIN AMERICA RECEIVING FIRST LINE PALBOCICLIB COMBINATIONS
FOR HORMONE RECEPTOR POSITIVE/ HUMAN EPIDERMAL GROWTH
FACTOR RECEPTOR 2 NEGATIVE (HR+/HER2-) ADVANCED/METASTATIC
BREAST CANCER IN REAL WORLD SETTINGS**

This document contains confidential information belonging to Pfizer. Except as otherwise agreed to in writing, by accepting or reviewing this document, you agree to hold this information in confidence and not copy or disclose it to others (except where required by applicable law) or use it for unauthorized purposes. In the event of any actual or suspected breach of this obligation, Pfizer must be promptly notified.

Study Information

Title	Treatment Patterns and Clinical Outcomes Among Patients in Latin America Receiving First Line Palbociclib Combinations For hormone receptor positive/ human epidermal growth factor receptor 2 negative (HR+/HER2-) Advanced/Metastatic Breast Cancer in Real World Settings.
Protocol number	A5481125
Protocol version identifier	Version 3.0
Date	13 August 2020
Date of last version of protocol	16 April 2019
Active substance	L01XE33 - Palbociclib
Medicinal product	Ibrance (palbociclib)
Research question and objectives	To describe patient demographics, clinical characteristics, treatment patterns and clinical outcomes of adult female patients who have received palbociclib combination treatments as first line therapy, regardless of combination partner and labelled use in real world settings across Latin America.
Primary objectives	
To describe demographics and clinical characteristics of patients who have received palbociclib combination treatment as a first line therapy, regardless of combination partner and labelled use.	
To describe adjuvant therapies received for the treatment of early or locally advanced breast cancer (Stages 0-IIIa).	
To describe treatments received in the advanced/metastatic setting, before and after palbociclib combination use.	
To describe dosing and dose changes, interruptions, and delays associated with palbociclib use in clinical practice.	

To detail supportive therapies received by patients while receiving palbociclib combination treatment.

To determine in overall population and defined subgroups, clinical outcomes including.

Proportion of patients who are progression free at specific intervals (eg, 6, 12, 18 months).

Objective response rate (ORR).

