7.1. Primary Objectives

- To describe the demographic and clinical characteristics of patients who have received palbociclib combination treatments as first line treatment, regardless of combination partner and labelled use.
- To summarize adjuvant therapies received for the treatment of early or locally advanced breast cancer (Stages 0-IIIa).
- To describe treatments received in the advanced/metastatic setting, before and after palbociclib combination use.
- To describe dosing and dose changes, interruptions, delays, and discontinuations associated with palbociclib use in clinical practice.
- To describe supportive therapies received by patients while receiving palbociclib combination treatments.
- To determine clinical outcomes including (but not limited to).
 - Proportion of patients who are progression free at multiple intervals (eg, 12, 18 months).
 - Objective response rate (ORR) - depending on availability of follow-up data.
 - Proportion of patients alive 1- and 2-year post palbociclib combination initiation - depending on availability of follow-up data.

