7.2. Exploratory Objectives

- To evaluate time to progression (TTP)/Progression Free Survival (PFS) associated with palbociclib combination treatments – depending on availability of follow-up data.

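### Could event-free patients with short follow-up be dropped as missing from the primary progression-free and survival proportions?

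*Combined protocol and SAP*

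**What the plan says.** The Study Information table lists as a primary outcome "Proportion of patients who are progression free at specific intervals (eg, 6, 12, 18 months"); section 7.1 has "Proportion of patients who are progression free at multiple intervals (eg, 12, 18 months"). Section 7.1 also lists "Proportion of patients alive 1- and 2-year post palbociclib combination initiation - depending on availability of follow-up data". Section 7.2 makes a separate, exploratory objective: "To evaluate time to progression (TTP)/Progression Free Survival (PFS) associated with palbociclib combination treatments".

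Section 8.7 sets methods by type of variable. Categorical variables get counts, percentages and the number missing. Time to event gets "A Kaplan-Meier chart that will visually estimate the distribution of times to some events"; the sentence goes on to name progression as the example and says that patients who have not yet had the event are allowed for. The next item under the same heading is "1-yr and 2-yr rates, median or some more appropriate percentiles if the median time is not reached in the sample". The section closes with the rule "Missing data will be excluded on a case by case basis and will not be imputed". It leaves detailed methods to a separate SAP, which is not among the documents, and adds that "any major modifications of primary endpoint definitions or their analyses would be reflected in a protocol amendment".

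**The concern.** A proportion can be read as a categorical variable or as a point on a survival curve, and the plan does not say which is meant. Three features point towards the categorical reading. Time to progression and progression-free survival, the obvious Kaplan-Meier endpoints, are set apart as exploratory. The rates listed beside the Kaplan-Meier chart are at 1 and 2 years only, so 6 and 18 months are not mentioned. The survival proportions depend on follow-up being available, and the missing-data rule excludes rather than imputes.

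Taken together and applied patient by patient, these would make availability depend on the outcome. A patient who progressed at month 5 has a known 18-month status; a patient event-free at month 17 does not. Excluding the second and keeping the first biases a primary outcome downwards. Counting the second as free biases it upwards. Colombia joins last with the shortest follow-up, so it would be hit hardest.

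**Working it through.** **Calendar check.** The inputs are Colombian availability in November 2018 (section 7), an index date 60 days after first prescription (section 8.1), a single review (section 8.2) and data collection from August to October 2020 (section 5). A month is 30.4375 days.

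- Longest: 1 Nov 2018 + 60 days = 31 Dec 2018; to 31 Oct 2020 is 670 days; 670 / 30.4375 = 22.0 months.
- Shortest maximum: 30 Nov 2018 + 60 days = 29 Jan 2019; to 1 Aug 2020 is 550 days; 550 / 30.4375 = 18.1 months.
- Without the 60-day lag: 1 Nov 2018 to 31 Oct 2020 is 730 days, one day short of the second anniversary.

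So on the stated milestones no Colombian patient can be observed alive at 24 months. The plan states no maximum follow-up or number at risk, so there is no figure of its own to reproduce here.

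**Size under the exclusion reading, 18 months progression free.** Assume exponential times with the 24.8-month median that section 6 quotes for PALOMA-2: h = ln 2 / 24.8, and true S(18) = exp(-18h) = 60.5%. Let C be a patient's available follow-up.

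- Known free = n × P(C ≥ 18) × S(18).
- Known progressed = n × mean of [1 - exp(-h × min(C, 18))].
- Exclusion estimate = known free / (known free + known progressed).

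Colombia, n = 200, C uniform from 6 to 22.0 months: free 30.3, progressed 62.0, unknown 107.7; 30.3 / 92.3 = 32.8%.

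All 847 records (647 collected + 200 expected), with country maxima of 43.6 months (Argentina), 38.0 (Mexico), 50.0 (Chile), 36.0 (Costa Rica), 25.0 (Panama), 39.0 (Peru) and 22.0 (Colombia). For the first six, the maximum runs from availability + 60 days to 30 Sep 2019, with availability on the first of the month except for Argentina's exact date.

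| Start dates | Known free | Known progressed | Exclusion estimate |
|---|---|---|---|
| Even, until 6 months before review | 289.8 | 293.0 | 289.8 / 582.8 = 49.7% |
| Within 12 months of earliest index date | 430.0 | 325.0 | 430.0 / 755.0 = 57.0% |
| Within 6 months | 471.8 | 333.7 | 471.8 / 805.5 = 58.6% |
| Within 4 months | 512.1 | 334.9 | 512.1 / 847 = 60.5% |

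Sections 8.1 and 8.2 tell physicians to go to the index date and take the next eligible patients in sequence, so that the window is long. That favours the lower rows. Physicians who first prescribed late would move the result back up the table. Kaplan-Meier on the evenly spread case returns 60.4% in simulation.

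**Size at 2 years, pooled.** Assume true survival of 75% (not from the documents) and, as a best case, full 24-month status for the other 647. Colombian deaths before review are 30.7, and 647 × 0.75 = 485.25; 485.25 / (647 + 30.7) = 71.6%. For true survival of 65% and 85% the results are 60.9% and 82.7%.

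**Which reading the text supports.** The 1- and 2-year rates stand under the time-to-event heading, next to a method described as allowing for patients without the event. That is censoring, and it covers both survival landmarks and, by time point, 12-month progression. Section 8.9 shows what missing data means in this study: eCRF questions must be answered before the next one opens, no blanks are expected, and unknown is an allowed answer. This is missingness of an item. Nothing in the plan calls short follow-up missing data.

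**The case for a change.** The strongest case for a change is that these are primary outcomes and the protocol should not leave their denominator to be inferred. No sentence ties the 6- and 18-month proportions to Kaplan-Meier. Section 8.6 adds that incomplete records may be excluded, Table 1 promises 1- and 2-year survival in subgroups without the condition in section 7.1, and section 8.8 foresees analysis by country. A short clarification would be cheap, and section 8.7 itself treats the protocol as the place for major changes to primary analyses.

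Part of this stands. The method for 6 and 18 months is not written down, and a Colombia-only 2-year rate cannot be estimated on the current dates. Neither makes the plan unsound. The 6- and 18-month values are examples in an open list, and they come from the same progression curve as the 12-month value. The country analysis is optional and subject to sample size. The survival proportions are conditional in section 7.1, and subject to sample size in the Study Information table. The abstract lets the Colombian dates depend on approval dates and the follow-up required, although reaching 24 months from the earliest index date would need review on 31 Dec 2020, at the end of the month planned for the final report.

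**Conclusion.** The concern does not call for a change. The calendar arithmetic is right, but the bias arises only if an analyst sets aside the censoring method that section 8.7 names and treats short follow-up as a missing answer. Read as written, Colombian patients count in the pooled risk set until they are censored, at 22.0 months or earlier, and the pooled curve beyond that rests on the other six countries. Writing Kaplan-Meier against each landmark would record what the plan already implies and would not alter a result.

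Under the reading rejected here, the illustrative pooled 18-month shortfall runs from 10.8 points (60.5 - 49.7) with evenly spread starts, through 3.5 points (60.5 - 57.0) with starts within 12 months, to none with starts within 4 months. These sizes assume exponential times and the same hazard in every country. The conclusion assumes that censoring is unrelated to prognosis and that each record gives the length of follow-up, which the eligibility minimum in section 8.2.1 requires the physician to know. The separate SAP was not available and may state the method outright.

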8.8. SUBGROUP ANALYSIS

Exploratory stratifications will be conducted to explore differences between, demographics, treatments, clinical characteristics, baseline co-morbidities or 'responders' and 'non-responders' to treatment, however these will be only descriptive in nature.

Responders and non-responders will be defined according to the best recorded response to palbociclib treatment.

Sample size permitting, additional stratifications may include:

- Analysis by country.

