The advantage to a retrospective medical record review approach over a database analysis is that of being designed specifically to collect data that fulfils the study objectives. Thus, it readily collects and informs on all key drug related clinical outcome measures of critical importance to this study, in a consistent manner, across countries. The resulting data set enables direct comparisons across markets, delivering in turn greater confidence in the reliability of conclusions drawn from the research. An additional advantage of this approach lies in the ability to obtain information that only the treating physician may be aware of, such as the reasons for treatment switches or discontinuations or more perceptive questions that rely on the physician's professional opinion.

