8.2. Setting

Upon study completion data will be collected from 7 countries. Approximately 30-40 physicians will be recruited in Colombia. Data will be collected retrospectively at a single point in time from patient medical records. To date, 6 physicians in Costa Rica, 1 in Panama, 1 in Chile, 15 in Mexico, 41 in Argentina and 5 in Peru completed eCRFs.

Screening questions/recruitment criteria will ensure the relevant physicians are selected and all other non-qualifying physicians will be excluded. In addition, a representative geographical split and private/public practice split for physicians will be sought where possible to ensure a representative sample.

To be eligible, physicians must have treated or be treating four or more HR+/HER2- ABC/MBC patients who meet the eligibility criteria for the study. This will ensure that recruited physicians will be able to complete the minimum number of eCRFs required to participate in the study. Once physicians have been recruited, they must go back to a specific index date, defined in [Section 7.1](#), and select the next 'n' number of eligible patient records from patients who have been treated with a palbociclib combination. The consecutive approach to recruitment will be stressed to each participating physician to limit selection bias. Physicians will confirm patient eligibility.

Patient records must meet the following criteria to be eligible for the medical record reviews. They must be female, over 18 years of age and they must have been diagnosed with HR+/HER2- ABC/MBC. Patients must have received palbociclib as a first line therapy. For the chart review, palbociclib and letrozole/aromatase inhibitor must have been initiated a minimum of 6 months prior to date of medical chart review, and palbociclib and fulvestrant must have been initiated a minimum of 3 months prior to date of medical chart review. This will permit the capture of meaningful clinical outcomes data.

A full list of the eligibility criteria can be found in [Section 8.2.1](#).

In order to ensure that sufficient data is captured for each indication, indication quotas will be enforced. This will be determined on a country by country basis.

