8.2.1. Inclusion Criteria

Physician inclusion criteria:

- Oncologist or gynecologist.
- Responsible for treating $\geq 4-10$ (depending on country) ABC/MBC patients who meet the eligibility criteria.
- Agrees to participate in the study and complete the CRFs within the data collection period.

Patient inclusion criteria:

- ≥ 18 years old.
- HR+/HER2- breast cancer diagnosis with confirmed metastatic or advanced disease.
- Received palbociclib as a first line therapy.
- No prior or current enrolment in an interventional clinical trial for ABC/MBC.
- Minimum of three months of follow up data since palbociclib with fulvestrant initiation, or minimum of six months of follow up data since palbociclib with letrozole/aromatase inhibitor initiation.

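### Best recorded response is summarised without regard to follow-up, while the minimum observation is 3 months with fulvestrant and 6 months with an aromatase inhibitor, which can lower ORR for fulvestrant

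*Combined protocol and SAP*

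**What the plan says.** ORR is one of the clinical outcomes under the primary objectives (Section 7.1), worded as "Objective response rate (ORR) - depending on availability of follow-up data". No section gives its response criteria, denominator, evaluability rule or time point. The nearest definition is in Section 8.8, for the exploratory responder split: "Responders and non-responders will be defined according to the best recorded response to palbociclib treatment".

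Section 8.2 has the data taken from the records at one point in time. Section 8.7 summarises categorical variables as "Number and percent (%) within each category", with a count of missing values. It reserves Kaplan-Meier, which allows for patients without the event so far, for time-to-event outcomes.

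The minimum observation in Section 8.2.1 differs by partner: "Minimum of three months of follow up data since palbociclib with fulvestrant initiation", but "minimum of six months of follow up data since palbociclib with letrozole/aromatase inhibitor initiation". Section 8.2 says of these minimums: "This will permit the capture of meaningful clinical outcomes data". It gives no time-to-response or assessment-interval figure in support.

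Table 1 (Section 8.3) makes the palbociclib combination a subgroup identifier and lists ORR among the outcomes reported within subgroups. Section 8.8 stratifies by treatment and by responder status.

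**The concern.** For a given patient, best response can only stay the same or improve as observation lengthens. A percentage with a best response therefore depends on how long patients were watched. The plan allows for incomplete follow-up when it describes progression and survival, but has no counterpart for response.

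Because the entry minimum is shorter for fulvestrant, only that group can contain patients seen for 3 to 6 months. Two things can happen to them:

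- A patient already assessed, for example with stable disease, has a recorded best response. That patient is not missing and is counted as a non-responder.
- A patient not yet assessed may be entered as unknown, which Section 8.9 allows, and excluded under the missing-data rule in Section 8.7. The denominator then depends on the window.

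The first effect makes fulvestrant look less active than it would with equal observation. It also puts patients with short follow-up among the non-responders, so short follow-up can look like one of their characteristics. Partner groups are likely to be set side by side, since Section 8.2 enforces quotas by indication to secure enough data for each.

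**Working it through.** The plan states no ORR assumption and no sample-size calculation, so there is no figure of its own to reproduce. The check is an illustration.

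**Inputs from the protocol.** Minimum windows of 3 and 6 months (Sections 8.2 and 8.2.1); approval dates (Section 7); collection dates (Section 5); index date 60 days after the physician's first prescription (Section 8.1).

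**Assumed inputs, not in the documents.** Eventual ORR p of 40–60%, the same for both partners. Time to response among eventual responders exponential with median m of 2–4 months. Follow-up uniform from the minimum to 12, 20 or 32 months.

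**Step 1. Share of eventual responses recorded by month t:** F(t) = 1 − 2^(−t/m).

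| m (months) | F(3) | F(6) |
|---|---|---|
| 2 | 0.646 | 0.875 |
| 3 | 0.500 | 0.750 |
| 4 | 0.405 | 0.646 |

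**Step 2. Gap for patients exactly at the two minimums:** p × [F(6) − F(3)].

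- Smallest: p = 0.40, m = 2 gives 0.40 × (0.875 − 0.646) = 9.1 points.
- Middle: p = 0.50, m = 3 gives 37.5% − 25.0% = 12.5 points.
- Largest: p = 0.60, m = 3 gives 0.60 × 0.25 = 15.0 points.

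**Step 3. Gap with follow-up spread out.** The mean of F over uniform follow-up from a to b is 1 − (m/ln 2) × [2^(−a/m) − 2^(−b/m)] / (b − a), with a = 3 for fulvestrant and a = 6 for the aromatase inhibitor. For p = 0.50, m = 3, b = 12:

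- fulvestrant: 0.50 × [1 − 4.328 × (0.5000 − 0.0625)/9] = 39.5%
- aromatase inhibitor: 0.50 × [1 − 4.328 × (0.2500 − 0.0625)/6] = 43.2%
- gap: 3.8 points before rounding the two rates

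Over all combinations of p and m:

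| Follow-up uniform to | Fulvestrant patients under 6 months, 3/(b − 3) | Artificial gap |
|---|---|---|
| 12 months | 33% | 2.2–4.9 points |
| 20 months | 18% | 1.4–3.5 points |
| 32 months | 10% | 0.9–2.4 points |

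**Step 4. Effect of a common minimum.** With a = 6 for both partners, and equal response curves and follow-up beyond 6 months, the gap is 0. If follow-up beyond 6 months differs, a gap remains: with p = 0.50 and m = 3, ORR is 37.5% at 6 months and 46.9% at 12.

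**Step 5. Country.** The longest possible window is the end of collection minus (approval date + 60 days), using the first of the month where only a month is given. This is 22.0 months in Colombia (to 31 October 2020) and, to 30 September 2019, from 25.0 months in Panama to 50.0 in Chile. With p = 0.50, recorded ORR at 22 months is 48.9% (m = 4) to 50.0% (m = 2), and at 50 months it is 50.0%. The difference is about 1 point or less.

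**The case against.** The strongest reply is that the plan does not commit to a faulty ORR analysis. The sentence in Section 8.8 defines an exploratory split, ORR itself is left undefined, and Section 8.7 defers detailed methods to a separate SAP. That is right as far as it goes: applying best response and a plain percentage to ORR is an inference from the only rules given. But those rules contain nothing that would protect ORR. The condition in Section 7.1 on available follow-up sets no minimum and no time point.

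A reader might infer that fulvestrant patients are scored as non-responders before any response could be seen. The documents do not support this. They give no assessment schedule, an unassessed patient can be recorded as unknown and dropped, and in the illustration 41–65% of eventual responses are already recorded by 3 months. What stands is narrower: a later response is missed in a patient already assessed.

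A reader might also take the 12-point figure as the expected bias. It holds only for patients exactly at both minimums. Section 8.1 starts selection soon after the physician's first prescription and proceeds consecutively, in order to lengthen observation. This favours longer follow-up, although the index date follows each physician's own first use, so late adopters will still contribute short windows.

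Finally, Section 8.1 claims that "The resulting data set enables direct comparisons across markets", and one might infer that country ORRs are distorted because Colombia's window is shorter. Step 5 shows that the maximum windows do not support that.

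The study is descriptive, has no comparator, and warns of channeling bias in Section 8.10. This limits the consequences, but that section does not mention unequal follow-up, and a descriptive percentage can still be biased.

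**Conclusion.** The point holds in a limited form, as a minor one. Under the rules given, ORR and the responder split depend on length of observation, and the unequal entry minimums can push ORR down for recently started fulvestrant patients. The direction rests on the protocol's own rules together with equal underlying response in the two groups.

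The size cannot be established from the documents. Under the stated assumptions it is about 9–15 points for patients at the minimums and about 1–5 points for whole groups with evenly spread follow-up. The real figure depends on the share of fulvestrant patients reviewed at 3 to 6 months, which is not given. No country effect follows from the maximum windows.

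**What to change.** In Sections 8.7 and 8.8, or in the SAP:

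- Base ORR by partner and the responder/non-responder split on patients who started palbociclib at least 6 months before chart review, whatever the partner.
- Select on start date, not on observed follow-up, so that enrolled patients who progressed or died early stay in the denominator. Section 8.2 already words its minimum by initiation date. Section 8.2.1 asks for follow-up data instead, and an analysis rule cannot bring back early deaths that were never enrolled on that reading.
- Report the all-patient ORR beside it, with the number of unknown responses and the median time from start to review, by partner and country.
- Keep the 3-to-6-month patients in the Kaplan-Meier analyses.

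The cost is analysis-plan wording. The eligibility check already needs the start and review dates, so no new data should be required, including for the 647 completed records. The downside is fewer fulvestrant patients in this ORR denominator. Follow-up beyond 6 months remains unequal, so subgroup ORRs should still be read with the follow-up shown.
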